6.3. Exclusion Criteria

A participant will not be eligible for inclusion in this study if any of the following criteria apply:

1. Participants with other types of AIHA (e.g., cold antibody AIHA, cold agglutinin syndrome, mixed type AIHA, or paroxysmal cold hemoglobinuria).
2. Participants requiring more than 2 units of RBC per week in the 2 weeks prior to Screening and Baseline.
3. Use of rituximab, any monoclonal antibody for immunomodulation, or proteasome inhibitor, within the past 3 months prior to Screening.
4. Immunoglobulins given by SC, IV (IVIG), or intramuscular route, or plasmapheresis/plasma exchange (PE) within 60 days before Screening.
5. Total IgG level <6 g/L (at Screening).
6. Absolute neutrophil count <1000 cells/mm³(at Screening).
7. Albumin level <3.5 g/dL at Screening.
8. Known advanced liver disease including any diagnosis of cirrhosis of any stage.

Non- alcoholic fatty liver disease (NAFLD) including non-alcoholic steatohepatitis (NASH) is allowable if there has been a recent (within 6 months) normal ultrasound, CT, or MRI. If the ultrasound, CT, or MRI demonstrate fatty changes alone, the participant may be enrolled if s/he has a normal range fibroscan for liver fibrosis.

9. AST or ALT $\geq 1.5x$ ULN at Screening.

The participant may only be enrolled if s/he has a recent (within 6 months) normal ultrasound, CT, or MRI. If the ultrasound, CT, or MRI demonstrate fatty changes alone, the participant may be enrolled if s/he has a normal range fibroscan for liver fibrosis.

10. Participant has any laboratory abnormality (at screening) that, in the opinion of the investigator, is clinically significant, has not resolved at baseline, and could jeopardize or would compromise the participant's ability to participate in this study.
11. Medical history of primary immunodeficiency, T-cell or humoral, including common variable immunodeficiency.
12. Have an active infection, a recent serious infection (i.e., requiring injectable antimicrobial therapy or hospitalization) within the 8 weeks prior to Screening.

13. History of or known infection with human immunodeficiency virus (HIV), hepatitis B virus (HBV), or Mycobacterium tuberculosis:
 - Participants must have negative test results for HBV surface antigen, HBV core antibody, HIV 1 and 2 antibodies, and a negative QuantiFERON-TB Gold test at Screening.
 - Participants with an indeterminate QuantiFERON-TB Gold test result will be allowed one retest; if not negative on retesting, the participant will be excluded.
14. Infection with hepatitis C virus (HCV):
 - Participants must have a negative test result for HCV antibody.

or

 - Participants with a known history of HCV must have documented evidence of sustained virologic response that is consistent with cure of hepatitis C infection. This is defined as undetectable or unquantifiable HCV RNA at least 12 weeks after stopping HCV treatment (HCV Guidance: Recommendations for Testing, Managing, and Treating Hepatitis C; 2014-2018, AASLD and IDSA). This should be confirmed with a negative HCV RNA test at Screening.
15. Active malignancy or history of malignancy in the 3 years prior to screening (exclusive of non-melanoma skin cancer and cervical cancer in situ).
16. Participant has any medical condition (acute or chronic illness) or psychiatric condition that, in the opinion of the investigator, could jeopardize or would compromise the participant's ability to participate in this study.
17. Body Mass Index (BMI) at Screening ≥ 40 kg/m².
18. Use of investigational drug within 60 days or 5 half-lives of the drug (whichever is longer) before Screening.
19. Participant has received a live vaccination within 2 weeks prior to the Baseline Visit; or intends to have a live vaccination during the course of the study or within 7 weeks following the final dose of study treatment.
20. History of sensitivity to any of the study treatments, or components thereof or a history of anaphylaxis (i.e., serious, life-threatening allergic reactions) that, in the opinion of the Investigator or Medical Monitor, contraindicates their participation.
21. Pregnant or lactating females as determined by positive serum or urine human chorionic gonadotropin test at screening or baseline.
22. QTcF interval >450 milliseconds for males and >470 milliseconds for females at Screening (a single repeat is allowed for eligibility determination). QTcF >480 msec in participants with Bundle Branch Block.
23. Diagnosis of concomitant idiopathic thrombocytopenia purpura (ITP)/ Evans syndrome with platelet count $<100,000$.

6.4. Other Eligibility Criteria Considerations

To assess any potential impact on participant eligibility with regard to safety, the Principal Investigator must refer to the following document(s) for detailed information regarding warnings, precautions, contraindications, AEs, and other significant data pertaining to the investigational product(s) being used in this study:

RVT-1401 Investigator's Brochure

6.5. Screening/Baseline Failures

Screen failures are defined as participants who consent to participate in the clinical trial but are never subsequently enrolled. A minimal set of screen failure information is required including date of informed consent, demography, screen failure details, eligibility criteria, and any SAEs. Screen failure data will be recorded within the electronic Case Report Form (eCRF).

6.6. Lifestyle Restrictions

6.6.1. Contraception

Female participants of childbearing potential must not become pregnant and so must be sexually inactive by abstinence or agree to use a highly effective method of contraception (i.e., pregnancy rate of less than 1% per year).

Abstinence

Sexual inactivity by abstinence must be consistent with the preferred and usual lifestyle of the participant. Periodic abstinence (e.g., calendar, ovulation, symptothermal, postovulations methods) and withdrawal are not acceptable methods of contraception.

Contraceptive Methods with a Failure Rate of <1%

Hormonal

- Female participants and female partners of male study participants stable for at least 4 weeks prior to screening on a combined hormonal contraception associated with inhibition of ovulation (oral, intravaginal, transdermal) PLUS a barrier method (i.e., condom or occlusive cap [diaphragm or cervical/vault caps]).
- Female participants and female partners of male study participants stable for at least 4 weeks prior to screening on a Progestogen-only hormonal contraception associated with inhibition of ovulation (oral, injectable, implantable) PLUS a barrier method (i.e., condom or occlusive cap [diaphragm or cervical/vault caps]).
- Female participants and female partners of male study participants using a hormonal contraceptive must also use a barrier method (i.e., condom or occlusive

cap [diaphragm or cervical/vault caps]) and should have been stable on their hormonal contraceptive treatment for an appropriate period of time (as determined by the product label or Principal Investigator) prior to the start of dosing to sufficiently minimize the risk of pregnancy at that point.

Long-Acting Reversible

- Female participants and female partners of male study participants with an Intrauterine device (IUD) or intrauterine system (IUS) that meets the <1% failure rate as stated in the product label.

Male Contraception

- Male partner sterilization (vasectomy with documentation of azoospermia) prior to the female participant's entry into the study, and this male is the sole partner for that participant. For this definition, “documented” refers to the outcome of the investigator's/designee’s medical examination of the participant or review of the participant's medical history for study eligibility, as obtained via a verbal interview with the participant or from the participant’s medical records.
- Sterilized male participants who have had vasectomy with documented azoospermia post procedure can be included.

Additional Considerations for Male Participants

- Non-sterilized male participants who are sexually active with a female partner of childbearing potential must use effective method of double barrier contraception. Male participants practicing true sexual abstinence (when this is in line with the preferred and usual lifestyle of the participant) can be included. In addition, male participants must be advised not to donate sperm during this period from signing of Informed Consent Form (ICF), throughout the duration of the study, and for 90 days after the last administration of study drug.

These allowed methods of contraception are only effective when used consistently, correctly and in accordance with the product label. The investigator is responsible for ensuring participants understand how to properly use these methods of contraception.

Participants must be completely informed of the unknown risks of pregnancy and agree not to become pregnant during the time they are participating in this study. If there is any question that a participant will not be reliable in the use of appropriate contraceptive methods, they should not be entered into the study.

6.7. Withdrawal Criteria

6.7.1. Reasons for Withdrawal

A Principal Investigator may discontinue/withdraw a participant from the study if any of the following criteria apply:

- Any clinical AE, laboratory abnormality, or other medical condition or situation occurs such that continued participation in the study would not be in the best interest of the participant.
- Participant pregnancy
- Significant protocol violation (e.g., non-compliance with concomitant medications)
- Behavioral or administrative issue
- Participant request to discontinue/withdraw consent for any reason. It is important to document whether the withdrawal of consent is primarily due to an AE, lack of efficacy, or other reason.
- Discontinuation of the study at the request of the Sponsor, regulatory agency or an Institutional Review Board (IRB)/ Independent Ethics Committee (IEC)
- Stopping criteria, as noted in Section 6.8

If a participant meets a withdrawal criterion during treatment, an Early Termination visit will be required (Section 6.7.2).

6.7.2. Participant Withdrawal Procedures

If a participant is prematurely discontinued from the study, the Principal Investigator must make every effort to perform an Early Termination Visit per Section 8.1, Time and Events Table and document the primary reason for withdrawal.

Should a participant fail to attend the clinic for a required study visit, the site should attempt to contact the participant and re-schedule the missed visit as soon as possible. The site should also counsel the participant on the importance of maintaining the assigned visit schedule and ascertain whether or not the participant wishes to and/or should continue in the study. In cases where the participant does not return for the rescheduled visit or cannot be reached to reschedule the missed visit, the site should make every effort to regain contact with the participant (3 documented telephone calls and if necessary a certified letter to the participant's last known mailing address) so that they can appropriately be withdrawn from the study with a primary reason of "Lost to Follow-up".

6.8. Safety Management Criteria for Individual Participants

6.8.1. Liver Chemistry Management Criteria

To ensure subject safety and enhance reliability in determining the hepatotoxic potential of an investigational drug, a standardized process for identification, monitoring and evaluation of liver events is to be followed.

The following two categories of abnormalities / adverse events are to be considered during the course of the study (irrespective of whether classified/reported as an AE or SAE):

1. Liver laboratory triggers. These require repeated assessments of the abnormal laboratory parameter
2. Liver events. These require close observation and follow-up monitoring. Contributing factors are to be recorded on the appropriate CRF(s).

Please refer to Appendix 2 Table 4 for complete definitions of liver laboratory triggers and liver events. Every liver event defined in Appendix 2 Table 5 to be followed up by the investigator or designated personnel at the trial site, as summarized below. Additionally, required actions in case of liver laboratory triggers and liver events are outlined in Appendix 2, Table 5 (Follow up requirements for liver laboratory triggers and liver events). Repeat liver chemistry tests (i.e. ALT, AST, TBL, PT/INR, ALP and G-GT) regularly to confirm elevation and follow trends.

The following additional follow up should also be considered:

- Obtain a more detailed history of symptoms and prior or concurrent diseases.
- Obtain a history of concomitant drug use (including non-prescription medications and herbal and dietary supplement preparations), alcohol use, recreational drug use, and special diets.
- Exclude causes of underlying liver disease, as specified in Section 6.3 Exclusion Criteria
- Perform imaging such as abdominal US, CT or MRI, as appropriate
- Obtain a history of exposure to environmental chemical agents.
- Consider gastroenterology or hepatology consultations.

All follow-up information and procedures performed must be recorded as appropriate in the CRF.

These liver chemistry repeats will be performed using the central laboratory. If results will not be available from the central laboratory, then the repeats can also be performed at a local laboratory to monitor the safety of the subject. If a liver event is subsequently reported, any local liver chemistry tests previously conducted that are associated with this event should have results recorded on the appropriate CRF.

6.8.2. QTc Withdrawal Criteria

- QTc prolongation defined as QTcF >500 ms, or an increase of QTcF >60 ms above baseline on the 12-lead ECG, confirmed (persistent for >5 minutes) on two repeated 12-lead ECGs

6.8.3. Albumin Monitoring Criteria

In addition to lowering IgG, treatment with RVT-1401 is also expected to reduce serum albumin levels (Section 3.3.3.3). The following criteria are to be used to guide study drug administration:

- Grade 2 (albumin levels 2.0 g/dL - 3.0 g/dL): If there are no accompanying clinical signs and/or symptoms, no action will be taken with study drug.
- Grade 3 (albumin levels <2.0 g/dL):
 - Subjects with no signs/symptoms: study drug should be interrupted until albumin reached a level of 2.5 g/dL, at which point it may be restarted
 - Subjects with signs/symptoms limited to peripheral edema managed with diuretics: study drug should be interrupted until albumin reaches a level of 2.5 g/dL, at which point it may be restarted.
 - Subjects with signs/symptoms requiring treatment beyond diuretics: discontinue study drug

Grade 4 albumin levels: permanent discontinuation of study drug

6.8.4. Other Individual Stopping Criteria

- Subject has signs or symptoms of a serious infective episode requiring hospitalization or iv antibiotic therapy.
- Participant has a severe systemic allergic reaction (i.e., anaphylaxis) to study therapy.

6.9. Toxicity Management Criteria

6.9.1. Toxicity Management Criteria (AEs, Cardiovascular, and Injection Site Reactions)

The severity of each AE will be graded and managed according to the criteria in Table 2 (CTCAE version 5.0). Study drug should be permanently discontinued for any grade 4 toxicity other than hemoglobin decrease. Management of hemoglobin < 7.0 g/dL or anemia in the presence of cardiovascular symptoms is described in section 6.9.2. For grade 3 TEAE not considered related to WAIHA signs/symptoms, study drug should be withheld. Study drug may only be restarted following a grade 3 TEAE after discussion with the medical monitor. Table 2 Criteria for Determining the Grade/Severity of Adverse Event Terms

Grade	Criteria
1/Mild	Asymptomatic or mild symptoms, clinical or diagnostic observations only; intervention not indicated
2/Moderate	Limiting age-appropriate instrumental activities of daily living; minimal, local, or noninvasive intervention as indicated
3/Severe or medically significant	Not immediately life-threatening; hospitalization or prolongation of hospitalization indicated; disabling; limiting self-care activities of daily living, intervention as indicated
4/Life-threatening	Life threatening consequences; urgent intervention indicated
5/Death	Death related to adverse event

Injection Site Reactions

Injection site evaluations will be made by clinical staff following administration of RVT-1401 as described below. Additional details related to the specific injection site location will be included within a study specific manual. If an injection site reaction is observed, a physician will characterize and document the reaction as an AE. Review of the injection site will continue until the AE is resolved. Symptomatic treatment (e.g., warm compresses, topical steroids, antihistamines if itching is present, or NSAIDs) may be provided for injection site reactions at the discretion of the Investigator.

The injection sites will be monitored for pain, tenderness, erythema and swelling. Each injection site reaction will be categorized using the intensity grading scheme presented in Table 3.

Table 3 Criteria for Determining the Grade/Severity of Injection Site Reactions

Grade	Criteria
1/Mild	Tenderness with or without associated symptoms (e.g., warmth, erythema, itching)
2/Moderate	Pain; lipodystrophy; edema; phlebitis
3/Severe or medically significant	Ulceration or necrosis; severe tissue damage; operative intervention indicated

Common Terminology Criteria for Adverse Events (CTCAE) Version 5.0 Published: November 27, 2017.

6.9.2. Management of Rescue Therapy

Rescue therapy during the first 8 weeks of the Treatment Period is permitted for participants with haemoglobin levels <7.0 g/dL or in the presence of signs/symptoms of myocardial ischemia, hypoxia, or TIA/stroke. Participants requiring rescue therapy after the Week 8 visit will be discontinued and an early withdrawal visit scheduled.

Blood Transfusion

The date, time, and number of units transfused should be recorded, along with the results of cross-match testing. Follow-up hemoglobin should be measured with 12 hours of the end of the transfusion. Hemoglobin values will be censored from efficacy analyses for the 2 weeks following a blood transfusion.

Prednisone/Prednisolone

Prednisone/prednisolone rescue (up to a 50% increase from baseline for up to 5 days), is permitted as per the rescue therapy guidelines (Section 6.9.2). The date, time, and dose should be recorded. Hemoglobin values will be censored from efficacy analyses for the 2 weeks following the last dose of prednisone/prednisolone rescue.

Dexamethasone

High dose dexamethasone (up to 40 mg daily for up to 4 days) is permitted as per the rescue therapy guidelines (Section 6.9.2). The date, time, and dose should be recorded. Hemoglobin values will be censored from efficacy analyses for the 2 weeks following the last dose of dexamethasone rescue.

IVIg and Plasma Exchange

Due to the mechanism of action for RVT-1401, the use of IVIG and Plasma exchange are not allowed.

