4. OBJECTIVE(S) AND ENDPOINT(S)

Objectives	Endpoints
Primary	

To examine the effect of RVT-1401 on proportion of responders (defined as Hb level $\geq 10\text{g/dL}$ with at least a $\geq 2\text{ g/dL}$ increase from baseline without rescue therapy or blood transfusions in the previous two weeks)
 
To assess the safety and tolerability of RVT-1401 in subjects with WAIHA
	
Proportion of responders at week 13
 
Assessment of safety and tolerability by analysis of adverse event (AE) data and changes from baseline in vital signs, ECGs, and clinical laboratory values

Secondary	

To examine the effect of RVT-1401 on change in Hb levels
	
Change from baseline in Hb levels

To examine the effect of RVT-1401 on time to response
	
Time to response

To examine the effect of RVT-1401 on change in hematocrit levels
	
Change from baseline in hematocrit levels

To examine the effect of RVT-1401 on proportion of participants with Hb levels in the normal range
	
Proportion of participants with Hb levels in the normal range at week 13

To examine the effect of RVT-1401 on time to achieving Hb levels in the normal range
	
Time to achieving Hb levels in the normal range

To examine the effect of RVT-1401 on change in fatigue
	
Change from baseline in FACIT-F score

To examine the effect of RVT-1401 on change in dyspnea
	
Change from baseline in Medical Research Council (MRC) breathlessness scale

To examine the effect of RVT-1401 on change in health-related quality of life
	
Change from baseline in EQ-5D-3L score

To assess the change in serum levels of total IgG & IgG subclasses (I-IV)
	
Change from baseline in levels of total IgG & IgG subclasses (I-IV)

To examine RVT-1401 PK following repeated doses in patients with WAIHA
	
Concentration of RVT-1401 pre-dose (C_{trough})

To assess the changes in LDH, bilirubin,
	
Change from baseline in LDH, bilirubin, and

haptoglobin
 
To measure anti-RVT-1401 antibodies following repeated doses in patients with WAIHA
	
haptoglobin
 
Immunogenicity determined by change from pre-dose in anti-RVT-1401 antibodies, and characterization of any anti-RVT-1401 to confirm neutralization potential

Exploratory
	
	

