10.2. Statistical Considerations

10.2.1. Analysis Populations

Intention-To-Treat (ITT) Population

All enrolled participants who take at least one dose of study medication will be included in the ITT population. Participants will be summarized by treatment group.

This will be the population for all PD parameters.

Safety Population

All participants who enroll in the study and receive at least one dose of study treatment will be included in the Safety Population. Participants will be summarized by actual treatment group.

This will be the population for the safety analyses, as well as for presentation and summarization of baseline/demographic characteristics.

Pharmacokinetic Population

The PK Population will include all participants who undergo PK sampling and have evaluable concentration-time data for analysis.

Pharmacodynamic Population

The PD population will include all participants who have baseline measure, along with a post baseline measure and receive at least one dose of study treatment.

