10.3.2. Primary Endpoint for Efficacy

The primary endpoint will be defined as the proportion of responders at Week 13. The Fisher's exact test will be used for the difference between the two treatment groups.

The analysis of the primary endpoint will be performed on ITT based on all available data, without using any imputation method for missing data.

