10.3.3. Secondary Endpoints for Efficacy

For each of the continuous secondary endpoints, the actual value, change from baseline and percentage change from baseline for all secondary endpoints will be summarized by visit and treatment group using the n, mean, SD, median, first and third quartiles, minimum, and maximum values. The comparison of the active arms (separately) will be performed using a Mixed Model for Repeated Measures (MMRM)/ Analysis of Covariance model with treatment, Visit, and baseline value in the model. The least square means of the treatment difference, standard errors, 95% CI and p-value for the treatment will be presented at each visit. A 2-sided alpha of 0.05 will be used to determine statistical significance for Treatment. If deemed appropriate, the two active arms may be combined to evaluate any treatment effect for the changes from the baseline.

For categorical secondary endpoints, the number of participants who meet the endpoint and the percentage will be summarized. The percentage will be calculated using those participants who had a value at the time point. Statistical testing may be performed between the two treatments using a Fishers Exact Test. If deemed appropriate, the two active arms may be combined to evaluate any treatment effect for the shift from the baseline.

The analyses of the secondary endpoints will be performed on ITT based on all available data, without using any imputation method for missing data.

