11.3. Time Period and Frequency for Collecting AE and SAE Information

- AEs will be collected from the time of informed consent through the follow-up period, at the timepoints specified in the Section 8.1, Time and Events Table.
- Medical occurrences that begin prior to any study procedure but after obtaining informed consent may be recorded on the Medical History/Current Medical Conditions section of the eCRF.
- All SAEs will be recorded and reported to the Sponsor within 24 hours of site awareness.
- Any SAEs assessed as related to study participation (e.g., protocol-mandated procedures, invasive tests, or change in existing therapy) or related to investigational product will be recorded from the time a participant consents to participate in the study up to and including any follow-up contact.

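### The planned Week 13 responder analysis states neither a denominator nor a scoring rule for participants discontinued for rescue after Week 8, and one of two open readings inflates the responder rate

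*Protocol*

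**What the plan says.** **Rescue.** Protocol Section 6.9.2 allows rescue during the first eight weeks of treatment when Hb falls below 7.0 g/dL or there are signs of myocardial ischemia, hypoxia or TIA/stroke. After that: "Participants requiring rescue therapy after the Week 8 visit will be discontinued and an early withdrawal visit scheduled." The same section adds: "Hemoglobin values will be censored from efficacy analyses for the 2 weeks following a blood transfusion." An equivalent two-week rule follows the last dose of rescue prednisone/prednisolone or dexamethasone.

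**Withdrawal.** Section 6.7.2 says that for a participant who leaves early "the Principal Investigator must make every effort to perform an Early Termination Visit". The Time and Events Table (8.1) has a single early withdrawal column and schedules nothing after it.

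**Endpoint.** A Week 13 responder needs Hb of at least 10 g/dL and a rise of at least 2 g/dL from baseline, "without rescue therapy or blood transfusions in the previous two weeks" (Section 4).

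**Analysis.** Section 10.3.2: "The analysis of the primary endpoint will be performed on ITT based on all available data, without using any imputation method for missing data." Section 10.2.1 defines the population: "All enrolled participants who take at least one dose of study medication will be included in the ITT population." Section 10.3.3, on categorical secondary endpoints only, says: "The percentage will be calculated using those participants who had a value at the time point."

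**SAP.** Section 2.2.1 repeats the responder definition and Section 6.2 repeats that only dates are imputed. Section 1 limits Version 3.0 to listings for Cohort 1.

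**The concern.** A participant who needs rescue in the last weeks of treatment has, in most cases, failed treatment. The protocol takes that person off the study with one further visit and sets aside the Hb values that follow rescue. It then asks for a Week 13 responder proportion from whatever data exist. The missing value is therefore a consequence of the outcome, and the primary analysis section does not say what to do with it.

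Two competent statisticians could report different primary results from the same data. If failures leave the denominator, the reported rate rises, and it rises more in the cohort with more late rescues. Section 3.3.1 intends the results to inform dosing and support a Phase 3 study, so both the rate and the comparison of doses matter. Replacement of early leavers, which Section 6.1 permits, does not put the lost failures back.

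There is a smaller safety side. Section 11.3 ties event collection to the visit table: "AEs will be collected from the time of informed consent through the follow-up period, at the timepoints specified in the Section 8.1." A late-rescued participant has no scheduled visit after early withdrawal, while Section 3.3.2 expects IgG to take 6 to 8 weeks to return to baseline.

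**Working it through.** The documents give no power calculation, response rate or cohort split, so there is no stated figure to reproduce. The check has four steps.

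**1. Does the responder definition already settle the scoring?** Baseline is Week 1, Day 1, so the Week w visit falls on Day 7(w−1)+1.

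- Week 8: 7×7+1 = Day 50
- Week 11: 7×10+1 = Day 71
- Week 13: 7×12+1 = Day 85
- Start of the two-week look-back: 85−14 = Day 71 (Days 69 to 73 with the ±2-day visit window)

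Rescue from about Day 71 onward is non-response under the definition, although 10.3.2 does not say that a censored or missing Hb is scored that way. Rescue after Day 50 and before about Day 71 lies outside the look-back. For that interval of about three weeks the definition gives no answer.

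**2. What denominators does the text permit?**

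- *All dosed (10.2.1 with 10.3.2):* a participant without a qualifying Week 13 Hb is simply not a responder. Rate = x/n.
- *Observed (10.3.2's no-imputation wording, with 10.3.3 carried over):* a participant without a Week 13 value is not counted. Rate = x/(n−k), where k is the number discontinued for rescue after Week 8.

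Neither document chooses between them, and no text maps the early withdrawal Hb to Week 13.

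**3. How far apart are the readings?** The ratio is [x/(n−k)] / [x/n] = n/(n−k) for any x > 0. It does not depend on x. With x = 0 both rates are zero and there is no bias.

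| n per cohort (assumed) | k = 1 | k = 2 |
|---|---|---|
| 6 | 6/5 = 1.20 | 6/4 = 1.50 |
| 8 | 8/7 = 1.14 | 8/6 = 1.33 |
| 10 | 10/9 = 1.11 | 10/8 = 1.25 |

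As rates with exact (Clopper-Pearson) 95% intervals, n = 8:

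| Responders x | All dosed | One dropped | Two dropped |
|---|---|---|---|
| 4 | 4/8 = 50.0% (15.7–84.3) | 4/7 = 57.1% (18.4–90.1) | 4/6 = 66.7% (22.3–95.7) |
| 2 | 2/8 = 25.0% (3.2–65.1) | 2/7 = 28.6% (3.7–71.0) | 2/6 = 33.3% (4.3–77.7) |

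**4. What happens to the planned Fisher test?** Take an illustrative 7/8 against 2/8: two-sided p = 0.041. Drop two late-rescued failures from the weaker cohort, giving 7/8 against 2/6: p = 0.091. The choice of denominator can move the p-value across 0.05, here by making the doses look more alike.

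**The case against.** The strongest reply is that the protocol already gives the right answer. Section 10.3.2 names the ITT population, which is everyone dosed, and response has to be shown affirmatively. A participant with no qualifying Week 13 Hb has not shown it, so x/n needs no imputation. The observed-value denominator appears only in 10.3.3, and its absence from 10.3.2 may be deliberate. This stands. A reader might infer that the protocol drops late-rescued participants, or that dropping them is the better reading. The documents do not support that: both readings are open.

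A reader might also infer that the bias always raises the rate or favors a dose difference. It is nil with no responders, and step 4 shows it can shrink a between-cohort difference. What holds is narrower: the observed denominator can never lower a cohort's rate, and it raises any rate above zero.

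The protocol leaves full details to the SAP (10.3), but Version 3.0 supplies no rule. SAP Section 1 says the study was paused with five Cohort 1 subjects: two completed Week 20, one terminated early after Week 3, and two were still on treatment. No discontinuation for rescue after Week 8 is reported. To say that a Cohort 1 result is biased would therefore go beyond the documents.

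On safety, it is tempting to say that these participants go unmonitored. They do not. The early withdrawal visit includes laboratory tests, ECG and IgG. Known events are followed to resolution or stabilization (11.7), clinically significant laboratory values are repeated (8.3.4), and related SAEs learned of later are reported (11). Healthy volunteers given weekly doses for four weeks had IgG in the normal range and within 30% of baseline by 5 weeks (3.3.3.3). What is missing is scheduled detection of new events.

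**Conclusion.** The point holds as an unresolved choice in the protocol's primary analysis. Late-rescued participants have no assured Week 13 Hb, and neither the denominator nor their score is stated. If they are left out, any non-zero responder rate is multiplied by n/(n−k). For an assumed 8 per cohort that is 1.14 with one such participant and 1.33 with two; over 6 to 10 per cohort and one or two dropped, it runs from 1.11 to 1.50. Cohort size, number of late rescues and number of responders are all assumptions. In the 8-per-cohort examples the shifted rates lie inside the exact confidence interval for the all-dosed rate. That limits what any one result could show, but it does not justify an analysis rule whose error within a cohort runs in only one direction.

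The correction is worth making before any resumption or Cohort 2. It alters nothing in SAP Version 3.0, which computes no responder rate.

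**What to change.** In Section 10.3.2, state that the denominator is all dosed (ITT) participants, and that anyone who needs rescue after Week 8, or who stops drug for lack of efficacy before Week 13, is a non-responder. Participants who stop for another reason, such as an adverse event, need not be failed automatically; a Week 13 Hb, where there is one, can be scored under the existing definition. Rescue thresholds and the handling of rescue in the first eight weeks stay as they are. The cost is amendment wording and a responder rate that may be lower.

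Optional and secondary: let participants who stop drug stay in the study for safety follow-up to about 8 weeks after the last dose, unless consent is withdrawn. Completers are seen at Weeks 13, 14, 16 and 20, which is 1, 2, 4 and 8 weeks after the Week 12 dose. Matching this needs a new schedule counted from the last dose. For a last dose at Week 9, the same intervals give Weeks 10, 11, 13 and 17; the table has no Week 17 visit, and it schedules no hematology at Weeks 10 or 12. The cost is a few extra visits for a few people. A Week 13 Hb collected this way would be descriptive and would not change the primary score of a late-rescued participant.
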